2. To evaluate (pharmacodynamic) effects of NAS ketamine on Patient Reported Outcomes (PROs), such as pain scores, side effects, depression, health-related quality of life, and functional status.

2a. To assess PROs as measured by the Numerical Pain Rating Score (NPRS), Side Effect Rating Scale for Dissociative Anesthetics (SERSDA), Montgomery Asberg Depression Rating Scale (MADRS), and Edmonton Symptom Assessment (ESAS), Eastern Cooperative Oncology Group (ECOG) and Patient-Reported Outcomes Measurement Information System (PROMIS) scales.

Secondary Outcomes

3. To determine opioid sparing effect of NAS ketamine.

[figure not shown]
3a. To document use of rescue medications prior to and during the study

3b. To evaluate total opioid consumption prior to and during the study.

If intranasal ketamine can be utilized for pain control in cancer patients, this could provide them with superior analgesia and better quality of life, without the risk of significant respiratory depression associated with opioid medications. We seek to obtain preliminary data via a clinical trial addressing safety, feasibility, and utility of this novel technique for the treatment of persistent uncontrolled cancer pain. These findings would be an important initial step towards testing the effectiveness of intranasal ketamine as a non-opioid medication for cancer pain used as potential maintenance outpatient therapy. These initial findings would be applied to a subsequent trial to determine the effectiveness and associated toxicities of ketamine in a larger sample of cancer patients, and address the compelling need to identify new, successful management therapies for cancer pain.

C.APPROACH:

C.1 Study design and methods:

C.2 Methods:

This is a prospective clinical trial to investigate the use of intranasal ketamine in patients with uncontrolled pain related to cancer or cancer treatment. The trial will be conducted in the Phase 1 Unit of the Winship Cancer Institute (WCI).

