intranasal doses of ketamine at 10 mg, 30 mg and 50 mg ²⁸. Therefore, for study purposes 10mg, 30 mg and 50mg of intranasal ketamine will be administered. Each visit will be two to seven days apart to avoid any accumulation of study doses. Subjects will be recruited at the supportive oncology clinic, oncology clinics, the pain clinic and Acute Pain Service at Emory. Subjects may be identified and contacted via telephone with information about the study prior to their next clinic appointment in order to allow time for them to consider the study. After informed consent has been obtained, study eligibility will be confirmed (see Table of Assessments). An appointment will be made for the Phase I Unit at Winship. A family member/friend must transport the patient home following drug administration, as driving for 24 hours post drug administration is discouraged. Written informed consent will be obtained prior to performance of study procedures, either while recruiting prior to study visit one or during the first study visit, prior to beginning the study. Subjects must meet all study eligibility criteria on Visit 1 prior to study treatment. Patients will be asked to return to the Phase 1 Unit for a total of 5 study visits. All study visits to the clinic will take place within six weeks or less. A telephone call visit will occur 14 days after the last dose of medication administered to follow any ongoing adverse events that occurred during the study period. If there are no ongoing adverse events at the end of visit five, the subject's participation will end at that time. Subjects may be reconsented if withdrawn early, at the discretion of the investigator, provided all eligibility requirements are met.

Table of Assessments

Assessments	Screening	Visit One	Visit Two	Visit Three	Visit Four	Visit Five	Telephone Call
Review of Inclusion/Exclusion	X						
Informed Consent	X						
Med Hx/Demographics	X						
Hemoglobin (if none within 3 months of Visit One)		X					
Urine pregnancy test-within one week of planned Visit (women of child bearing potential)		X	X	X	X	X	
PHQ9 Depression Screening	X	X ¹					
Completion of PROMIS Questionnaire		X				X	
ECOG score		X	X	X	X	X	
ESAS		X	X	X	X	X	
MADRS ^{2,3}		X	X	X	X	X	
Height		X					
Weight		X	X	X	X	X	
IV access		X	X ⁴	X	X		
Study Medication Administration		X	X	X	X		
Vital Signs(HR ⁵ , BP, RR, Pulse Oximetry ⁶)		X ⁷	X ⁷	X ⁷	X ⁷	X ⁸	
Blood Samples (PK)		X ⁹	X ^{9,10}	X ^{9,10}	X ^{9,10}	X ¹⁰	
Hepatic Function test		X				X	

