2. Determine pharmacodynamics of intranasal ketamine in terms of Patient Reported Outcomes

- i. Pain scores on NPRS will be analyzed by Wilcoxon signed-rank test as the study sample size is too small to be analyzed by paired t test. Generalized Linear Model will be used to model any time trend for pain score change and to test if the trend is significant.
- ii. T-test will be used to compare any changes in depression severity on MADRS.
- iii. Chi-square test will be used to test presence/absence of any side effects. Wilcoxon signed rank test will be used to assess the severity of all the side effects (including SERSDA), if needed.
- iv. Paired T-test will be used to asses any changes in functional status on PROMIS scale.
- v. T-test will be used to compare any changes in ESAS and ECOG.

3. Determine PK-PD relationships of NAS ketamine delivered

Timing, degree and duration of change in pain scores will be compared with individual and group pharmacokinetic parameters to assess potential relationships between measures of exposure (C_{max} , and AUC_{0-t}) and pain relief. Multivariate modeling including patient-specific data (age, sex, weight, BMI, morphine equivalents) will be performed using initial PK parameters and goodness of fit analyses for compartmental model selection. If applicable, data from vital sign measurement changes will also be used as comparison with pharmacokinetic data.

4. Determine opioid sparing effect of intranasal ketamine.

- i. Chi-square test will be used to compare frequency of rescue medication use.
- ii. T-test will be used to compare total opioid consumption.

C.13 Data and Safety Monitoring and Reporting Plan:

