7. The Emory University School of Medicine Department of Anesthesiology will conduct this study according to national rules, regulations and guidelines governing human clinical research. In addition,

procedures cited by the US Code of Federal Regulations (Title 21) will be followed as these apply to the principles of Good Clinical Practice and approval by the Emory University Institutional Review Board (IRB).

Confidentiality: The privacy of the research subjects will be ensured through the standard procedures for securing research data. All records identifying the subject will be kept confidential and, to the extent permitted by the applicable laws and regulations, will not be made publicly available. Subjects will be identified by a study number. If the results of the study are published, the subject's identity will remain confidential.

C.14 Potential Pitfalls:

Lack of blinding/Lack of placebo arm. There is enough evidence to support an analgesic effect of ketamine. Since the study is being conducted in cancer pain patients and involves blood draws and transport, a placebo arm is considered to be unethical in these circumstances. The possibility exists that **ketamine might have long term effects beyond its duration of action** and the pain scores might be significantly lower than the compared to at the beginning of the study. In this case **change in pain score may not be significant during the later study visits**. However, overall this would be a good effect for pain control and can future studies can be designed to account for this effect. As cancer pain can be evolving and changing, the decision was made to finish all the study visits in the least possible duration of time, as possible. Once feasibility and safety is established with this study, the aim of future studies will be allow patients to take this medication at home for maintenance. **Lack of standard opioid regimen** among patients could be problematic in terms of comparison of outcomes.

E. REFERENCES/BIBLIOGRAPHY

1. van den Beuken-van Everdingen, M. H. *et al.* Prevalence of pain in patients with cancer: a systematic review of the past 40 years. *Ann Oncol* **18**, 1437-1449, doi:10.1093/annonc/mdm056 (2007).
2. Malinovsky. Ketamine and norketamine plasma concentrations after i.v., nasal and rectal administration in children. *Br J Anaesth* , 77(72):203-207 (1996 Aug;).

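### Opioid sparing: the tests in C.12 item 4 do not fit a before/during comparison in the same patients, and neither a per-day unit nor a pre-study window is stated

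*Combined protocol and SAP*

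**What the plan says.** Aims 3a and 3b (Objectives, Secondary Outcomes) are "To document use of rescue medications prior to and during the study" and "To evaluate total opioid consumption prior to and during the study". C.12 item 4 gives the whole analysis in two lines: "Chi-square test will be used to compare frequency of rescue medication use" and "T-test will be used to compare total opioid consumption". There is one group; C.14 explains that "a placebo arm is considered to be unethical in these circumstances".

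On the length of the study period, C.2 says "Each visit will be two to seven days apart to avoid any accumulation of study doses" and "All study visits to the clinic will take place within six weeks or less".

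On data sources, the Table of Assessments marks rescue-use details, pain diary and opioid pill count at Visits One to Five and none at screening. C.2 ties the diary to the time on trial, and the pill count and prescription-database search to intake during the study. Consent may be given "either while recruiting prior to study visit one or during the first study visit", so the diary need not cover any day before the first dose. C.8 contains per-day figures (breakthrough use per 24 hours, 50 mg/d morphine equivalent) and a stable regimen of more than 7 days. These are eligibility criteria; no text names them as the baseline.

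Elsewhere in C.12, item 2.iv specifies a paired test for PROMIS, and item 2.i chooses signed-rank for pain because the sample is considered too small for a paired t-test.

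**The concern.** Three things are left open that decide what the opioid-sparing result means.

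- **The rescue test.** Before and during values from the same patient are correlated. A chi-square test treats them as coming from different people.
- **The unit for opioids.** A total over a period grows with the length of the period, and time on study differs between patients.
- **The comparison period.** Without a fixed pre-study window, the before side of the comparison has no defined length.

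This is the only secondary outcome, and the protocol intends its findings to inform a larger trial. A change produced by window length would carry forward as a signal about ketamine.

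**Working it through.** The documents give no power, variance or expected change for opioid sparing, so there is no figure of the plan to reproduce. The only power statement (C.7) concerns the pain score.

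**1. Length of the study period.** Visit 1 to Visit 5 is four intervals of 2 to 7 days (C.2): 4 × 2 = 8 days to 4 × 7 = 28 days. The six-week limit allows 42 days. At constant daily use, totals therefore differ between patients by 28/8 = 3.5-fold, or up to 42/8 = 5.25-fold.

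**2. During/before ratio with no change in daily use.** If the total is a sum over each period, the ratio is (days on study)/(days in pre-study window). The window is not stated, so 7, 14 and 28 days are assumptions.

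| Pre-study window | 8 days on study | 28 days | 42 days |
|---|---|---|---|
| 7 days | 8/7 = 1.14 | 28/7 = 4.0 | 42/7 = 6.0 |
| 14 days | 8/14 = 0.57 | 28/14 = 2.0 | 42/14 = 3.0 |
| 28 days | 8/28 = 0.29 | 28/28 = 1.0 | 42/28 = 1.5 |

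A real 30% cut over 28 days against a 7-day window gives 0.7 × 4.0 = 2.8, an apparent near-tripling. Pairing does not help, because each patient's own difference contains the same imbalance.

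**3. Illustrative error rates for a paired t-test on totals.** Assumptions: n = 10; patient daily dose log-normal with CV 50%; day-to-day CV 20%; mean change nil, with a between-patient CV of change of 20% or 40%; intervals uniform on 2 to 7 days (mean 18 days in all); 20,000 runs; two-sided 5%.

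- 7-day window: false increase in 99.7% or 97% of trials.
- 28-day window: false sparing in 98% or 82%.
- 18-day window (equal to the mean time on study): about 5–6% in total.
- 7-day window with visits only 2 to 3 days apart: false increase in 92% or 43%.
- Signed-rank on mg/day with 2-to-7-day spacing: 5.0–6.6% across these windows.

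**4. Chi-square with one yes/no pair per patient.** Assumptions: n = 10, 50% answering yes in each period, latent correlation ρ. The chance of yes in both periods is 1/4 + arcsin(ρ)/(2π), that is 0.298, 0.333 and 0.373 at ρ = 0.3, 0.5 and 0.7. Summing over all possible tables, the nominal 5% uncorrected test rejects about 2.4%, 1.4% and 0.5% of the time when nothing has changed. In this form it is conservative.

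A plain yes/no on any rescue use would also carry little information. At an assumed one dose per day (Poisson), 1 − exp(−7) = 99.9% of patients have a dose within 7 days.

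**The case against.** The strongest reply is that the gap is one of wording. Total opioid consumption can mean scheduled plus rescue opioids together, not a sum over time, and the protocol's only opioid dose threshold (C.8) is already per day. The T-test may be meant as paired. A pre-study reference partly exists: C.3 item 9 records whether rescue was taken at the usual interval or longer, and the prescription-database search and Visit One pill count are planned. C.14 aims to finish visits quickly, and C.8 requires a stable regimen, so spread in time on study and in daily dose may be smaller than simulated.

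Much of this stands. It limits the size of the claim but does not supply the missing statements: no text in C.12 divides by days, names a window or says paired in item 4. If a paired t-test is meant, item 2.i already calls the sample too small for one.

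Four stronger readings are tempting and not supported:

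- **That an unpaired t-test is prescribed.** It is not; pairing is unstated. Under assumption, an unpaired test on per-day values would cut 80% power to 58% at a before/during correlation of 0.5, but the text does not require it.
- **That chi-square inflates false positives.** That needs doses pooled across patients (13% or 31% at 5 doses/day, 7-day windows and change CV 20% or 40%). The plan does not say doses will be pooled.
- **That the simulated rates are properties of the plan.** They hold only if the total is a sum over unequal periods, and they move with the assumed window, spacing and variability.
- **That the same fault runs through the rest of C.12.** For side effects the contrast is unstated; for MADRS, ESAS and ECOG, changes are most naturally read as paired; for the pain trend no linear slope is specified. These do not belong to this point.

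**Conclusion.** The point holds for C.12 item 4. A chi-square test does not fit a within-patient before/during comparison. The T-test on totals lacks a unit, a window and a statement of pairing.

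The firm part is arithmetic: if totals are period sums, unchanged daily use gives ratios from 1.14 to 6.0 (assumed 7-day window) or 0.29 to 1.5 (assumed 28-day window). The error rates are illustrative. The weight is moderate, since this is an unpowered secondary outcome of a preliminary study, and the pain-score signed-rank test does not depend on it. It should be corrected because the plan taken at its word can point in the wrong direction, and a baseline that is not collected at the time is hard to recover later.

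**What to change.** In C.12 item 4:

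1. **Rescue use.** Replace chi-square with a signed-rank test on each patient's change in rescue doses per day. If a yes/no outcome such as the C.3 item 9 record is kept, use exact McNemar.
2. **Opioids.** Replace the total with each patient's change in mg oral morphine equivalent per day, by paired signed-rank with a confidence interval.
3. **Windows.** Fix both, for example the 7 days before Visit One (in line with the stable-regimen criterion in C.8) against Visit 1 to Visit 5, each divided by its own number of days. Take the opioid baseline from the planned database search and Visit One pill count, and the rescue baseline from a recall item at Visit One.

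**Cost.** A few lines in C.12 and one added question; no change to visits or sample size. Patients already treated without a rescue baseline drop out of that test.

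**Limits to state.** Prescription fills are only a proxy for intake, and recall differs in mode from a diary. Patients may enter on high rescue use, so regression to the mean can look like sparing. The required 120 minutes after immediate-release opioid (C.2) may itself lower use on dosing days; consider a sensitivity analysis without those days. Results should therefore stay descriptive.

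Power is modest. For a 30% rescue cut, signed-rank has 84–86% or 61–63% (7-day windows, change CV 20% or 40%). Exact McNemar is demanding at n = 10: five discordant patients all in one direction give p = 2 × 0.5⁵ = 0.0625, so at least six are needed (2 × 0.5⁶ = 0.031). For a shift from 20% to 70% its power is 37–38%, against 62–64% for chi-square, which is a reason to prefer the per-day outcome.

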Cardiovascular effects: Potential effects include: increases in heart rate, systemic arterial pressure, systemic vascular resistance, pulmonary artery pressure, and pulmonary vascular resistance. In the absence of autonomic control, ketamine has direct myocardial depressant effect, usually overridden by central response. If >20% variation from baseline is noted in heart rate or blood pressure, study MD will be notified. Risk assessment will be done by the MD and appropriate medications will be given as deemed necessary. Patient will be admitted to inpatient medical oncology service for 23 hours observation if at the end of study visit a >20% variation persists despite treatment; HR >120; hypertensive urgency/emergence occurs. Hypertensive urgency is defined at SBP>180 or DBP>110. In hypertensive emergency signs or symptoms of end organ damage are noted such as blurry vision, headache, and chest pain.

Central nervous system effects: Include- tremors, increased intracranial pressure, floating sensation, hallucinations (auditory and visual), delirium, vivid dreams or illusions, confusion, restlessness, disorientation, dysphoria, dizziness, and sedation. After discontinuation of ketamine, recurrent illusions (flashbacks) can occur. Ketamine can lower the seizure threshold, especially in patients on aminophylline. Benzodiazepines such as midazolam 0.5 mg to 5 mg IV or lorazepam 0.5 mg to 5 mg IV or diazepam 0.5 mg to 10 mg IV or oral, etc. may be given to mitigate CNS side effects at the discretion of the study MD. Admission for 23 hours observation to the inpatient medical oncology service will be considered if at the end of a study visit either excessive sedation is noted or RASS score between -3 and -5 or if any severe psychological manifestations exist.

Gastrointestinal system effects: Include nausea, vomiting and increased salivation (due to increased salivary and tracheobronchial mucous gland secretions). Nausea and/or vomiting will be treated with

ondansetron 4 to 8 mg IV or PO depending upon severity. Diphenhydramine 6.25 to 25mg IV may be given, if no relief from ondansetron or if ondansetron is contraindicated. For increased salivation, not well tolerated by the patient, glycopyrrolate 0.2mg IV may be given if deemed necessary by the study MD. Admit if unable to tolerate oral liquid at the end of visit.

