1. This study will be followed by the Winship Cancer Institute Data Safety Monitoring Committee (DSMC) for local review and confirmation of proper study execution and safety measures. Initial study monitoring will occur within 6 months from the date of the first subject accrued, with 2 of the first 5 subjects reviewed. Therefore, subsequent monitoring will occur in six month intervals if any subjects were accrued. The population continuing to receive intervention will be monitored as determined by the DSMC. At minimum, 10% of subjects accrued since previous monitoring will be reviewed. An additional subject (or subjects) may be selected based on previously noted monitoring deficiencies or at DSMC discretion. Continued monitoring will occur in six month intervals for the population continuing to receive intervention as determined by the DSMC.

The DSMC will review pertinent aspects of the study conduct including patient safety, protocol compliance, data collection, and efficacy. The PI or designee will be responsible for notifying the DSMC of patient accrual and status updates within two months of the planned review.

- 2. Procedures to assure data integrity and protocol adherence:**

- a) A monthly meeting of investigators, clinical research coordinators and regulatory personnel will be held to review the clinical data.
- b) Adverse event reporting will utilize the Common Terminology Criteria for Adverse Events (CTCAE) version 5.0. The grading scale for these adverse events is as follows:
Grade 1 Mild; asymptomatic or mild symptoms; clinical or diagnostic observations only; intervention not indicated.

Grade 2 Moderate; minimal, local or noninvasive intervention indicated; limiting age appropriate instrumental activities of daily living (ADL)

Grade 3 Severe or medically significant but not immediately life-threatening; hospitalization or prolongation of hospitalization indicated; disabling; limiting self-care ADL

Grade 4 Life-threatening consequences; urgent intervention indicated

Grade 5 Death related to AE.

c) A serious adverse event (SAE) is an AE or suspected adverse drug reaction that fulfills one of the following:

- results in death
- is immediately life-threatening (life-threatening in the definition of SAE refers to an event in which the subject was at immediate risk of death at the time of the event; it does not refer to an event which hypothetically might have caused death if it were more severe).

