- requires in-subject **hospitalization** or prolongation of existing hospitalization
- results in persistent or significant **disability** or incapacity
- is a **congenital anomaly** or birth defect
- is an important medical event: important medical event in the definition of “serious” refers to those events which may not be immediately life-threatening, or result in death, or hospitalization, but from medical and scientific judgment may jeopardize the subject and/or may require medical or surgical intervention to prevent one of the other outcome listed above. Examples of such events are intensive treatment in an emergency room or at home for allergic bronchospasm, blood dyscrasias or convulsions that do not result in hospitalization. Development of cancer or drug dependency or drug abuse will normally be considered serious by this criterion.

d) Study progress in terms of enrollment and activity of current patients will be reviewed during the monthly meeting of the investigators, clinical research coordinators and regulatory personnel. The PI may increase the frequency of this meeting if necessary.

e) Study specific training of all study personnel, including management of potential adverse events, will occur prior to initiating study enrollment using the final approved protocol and study specific standard operating procedure document. Training of the Phase I staff will be conducted by the team clinical research coordinator prior to study enrollment. Completion of training will be documented on a study training log and stored in the regulatory binder. Investigators will complete CITI training as well as any additional training required by the Emory Office for Clinical Research.

3. Clinical monitoring will occur as previously described (Study Methods).

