4. As the IND sponsor-investigator, unexpected fatal or life threatening suspected adverse reactions will be reported using the Medwatch FDA form 3500A via FedEx to the FDA no later than 7 calendar days after the initial receipt of information (21CFR 312.32(C)(2)). Additionally, serious, unexpected suspected adverse reactions and a clinically important increase in the rate of a serious suspected adverse reaction will be reported to no later than 15 calendar days after determining the information qualifies for reporting (21 CFR 312.32 (C) (1)) in paper format using FDA form 3500A. Finally, an annual progress report will be provided within 60 days of the anniversary date that the IND became active , January 20, 2017, (21 CFR 312.33).
5. Patient data will be evaluated by the PI on an ongoing basis during the study visits to observe for any trends in adverse effects of the study treatment, to ensure continued subject safety and to ensure the scientific validity of the trial. Adverse events (AE) will be recorded. An adverse event is defined as any untoward medical occurrence in a patient or clinical investigation subject administered a pharmaceutical product or study treatment and that does not necessarily have a causal relationship with this administration. An AE can therefore be any unfavorable and unintended sign (including any abnormal laboratory findings), symptom, or disease temporally associated with the use of a medicinal (investigational) product, whether or not related to the medicinal (investigational) product. Adverse events will be captured from the time of the first study drug administration through the fifth study visit. Ongoing adverse events at the fifth visit will be followed with a telephone call visit 14 days (plus or minus 1 day) after the last medication administration. AEs will be reported to the PI by Emory email or telephone. All adverse events will be documented in an AE log. The reporting policy of the Emory IRB will be followed.
6. The study will be stopped after a hospitalization that is related to study drug administration for a formal review by the PI and the DSMC. When a hospitalization related to study drug administration occurs, the study will be put on hold. The PI or delegated person will communicate the event details to the DSMC for their review and determination of approval to continue the study. The study will be ended if there is more than one hospitalization related to the study drug administration.

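### The written study hold is triggered only by a drug-related hospitalization, so a drug-related death, life-threatening event or convulsion without admission triggers none

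*Combined protocol and SAP*

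**What the plan says.** Section C.13, item 6 states the hold twice, with the same trigger each time: "The study will be stopped after a hospitalization that is related to study drug administration", and then "When a hospitalization related to study drug administration occurs, the study will be put on hold". Release lies with the DSMC: "The PI or delegated person will communicate the event details to the DSMC for their review and determination of approval to continue the study". A second drug-related hospitalization ends the study.

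Item 2c of the same section defines a serious adverse event more broadly. Besides hospitalization, an event qualifies if it "results in death" or "is immediately life-threatening", or if it is an important medical event. Among the examples of the last kind are "blood dyscrasias or convulsions that do not result in hospitalization".

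Section C.5 recognizes a relevant risk with this drug: "Ketamine can lower the seizure threshold, especially in patients on aminophylline".

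**The concern.** The hold depends on whether the patient was admitted, not on how serious the event was. The protocol accepts in item 2c that an event can be serious without admission, then leaves such events out of the rule that pauses dosing and sends a single event to the DSMC.

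If the text is followed as written, other patients may go on being dosed after a drug-related death or convulsion without admission until someone chooses to pause. The person best placed to choose is the investigator, who also holds the IND as sponsor. A prespecified hold means the pause does not rest on that one judgment.

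**Working it through.** The plan gives no operating characteristics for this rule, so there is no figure to reproduce. The check compares the texts, followed by a simple count of doses.

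**Step 1: item 2c against item 6.** Each event below is assumed to be drug-related.

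| Event | Serious under item 2c | Hold under item 6 |
|---|---|---|
| Hospitalization | Yes | Yes, DSMC decides on release |
| Death outside hospital | Yes | None stated |
| Life-threatening event reversed in the unit, no admission | Yes | None stated |
| Convulsion, no admission | Yes, named as an example | None stated |

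**Step 2: does another provision supply the hold?**

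- C.13 item 5: "Patient data will be evaluated by the PI on an ongoing basis during the study visits". No trigger or hold is attached.
- C.13 items 2a and 2d: monthly team meetings, which the investigator may make more frequent. No hold is stated.
- C.13 item 4: FDA reports within 7 calendar days for unexpected fatal or life-threatening reactions, and within 15 for other serious unexpected ones. Item 5 adds the IRB reporting policy. These are reporting duties, and the 7- and 15-day limits for single events apply only to unexpected reactions.
- C.13 item 1: DSMC monitoring at six-month intervals, with routine updates tied to the planned reviews.
- C.2, Dose Finding: the 30 mg and 50 mg doses are withheld from a patient who had a severe adverse event at a smaller dose. This looks only at that patient's own history.

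None of these states a study-level hold.

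**Step 3: do the admission rules close the gap?** C.5 requires or considers admission in several situations, but most of them depend on the patient's state at the end of the visit. An event that has resolved by then need not lead to admission. For tonic-clonic movements C.5 gives notification of the study physician, monitoring and treatment, with no admission stated. A death after discharge lies outside these rules.

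**Step 4: exposure of another patient.** Inputs from C.2: four dosing visits, 2 to 7 days apart. Assumption: the event is on day 0 and another patient's visit 1 is on day 1. Dose k then falls on day 1 + (k − 1) × gap.

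| Gap | Dose days | Doses by day 7 | Doses by day 15 |
|---|---|---|---|
| 2 days | 1, 3, 5, 7 | 4 | 4 |
| 7 days | 1, 8, 15, 22 | 1 | 3 |

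From first to fourth dose there are 3 gaps: 3 × 2 = 6 days to 3 × 7 = 21 days. All four doses are therefore given by day 7 to day 22, possibly before the next monthly meeting. The spacing is nominal, because C.2 lets the clinic visits run over up to six weeks and visits can be rescheduled.

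**The case against.** The strongest reply is that the gap is narrower than it looks.

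- **Admission thresholds are low.** C.5 sends patients for 23-hour observation for, among other things, a heart rate above 120, hypertensive urgency, or respiratory depression persisting at the end of the visit. C.3 adds discharge criteria at 240 minutes. If observation stays count as hospitalizations, item 6 would fire often. The protocol does not say whether they count, and even on the broad reading a death at home or a resolved convulsion is missed. That reading would also let an admission for vomiting hold the study when a death outside hospital does not.
- **Seizure risk is reduced.** Exclusion 7 removes patients with a history of seizures or raised intracranial pressure, and the C.5 warning singles out aminophylline. This lowers the risk without removing it. C.4 also reports no serious side effects at intranasal doses up to 50 mg. That stands: these events should be rare.
- **Discretion remains.** Nothing bars the investigator, DSMC, IRB or FDA from pausing the study, and the IRB policy and the study's operating procedures were not available to check. This also stands, and it limits the finding to the protocol text. It does not explain why hospitalization gets a prespecified hold and death does not.
- **The dose count is a worst case.** It supposes that nobody intervenes and that the FDA limits are used in full. It shows what the text permits, not what is likely.
- **The remedy leaves an asymmetry.** Two drug-related deaths outside hospital would still not force the study to end, while two hospitalizations would. That is true, but under the fix each death would stop dosing until the DSMC approved continuing. Item 2c also takes in non-acute events such as drug dependency. A related one would trigger a hold, which the DSMC could release.

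**Conclusion.** The concern holds and should be fixed. Item 6 is the only study-level hold in the protocol, and both its hold sentences and its event-driven DSMC referral require a drug-related hospitalization. Three kinds of event at least as serious, or named as serious by the protocol itself, trigger neither.

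The size is one of timing: 1 to 4 further doses to a newly starting patient by day 7 and 3 to 4 by day 15, assuming a start on day 1, nominal visit spacing and no discretionary pause. The documents give no event rate and none is assumed, so no expected harm can be calculated. The conclusion on the missing trigger rests on the wording alone and does not depend on the dose count.

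**What to change.** In the two hold sentences of C.13 item 6, replace *hospitalization* with *serious adverse event as defined in item 2c (hospitalization included)*. Keep the requirement that the event be related to study drug, so that events of the underlying cancer stay outside the rule, and keep the DSMC's decision on whether to continue. Leave the ending rule (more than one drug-related hospitalization) as it is.

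The cost is an amendment to two sentences and an occasional extra hold for a drug-related serious event without admission, which the DSMC can release. With the ending rule unchanged, mandatory termination becomes no more likely.
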